The primary outcome of this study will be the percentage of individuals who received an initial vaccination within two weeks of a study intervention. Vaccine uptake will be primarily assessed by verbal confirmation of recent vaccination during a follow-up visit with a study team member. We will ask for visual documentation of the vaccine card or receipt that demonstrates the vaccine has been administered. Any participants lost to follow-up will be presumed "Unable to determine." A secondary outcome will be the number of individuals that complete their primary vaccination series within 6 weeks of their first dose.

In addition, data from the vaccine-uptake survey will analyzed for trends in willingness to vaccinate within participants. Changes promoting vaccine willingness could be indicative of an impactful vaccine intervention.

E Statistical Plan

Statistical considerations

Primary analysis

Our primary hypothesis is that the initial strategy of peer counseling will result in the highest vaccine uptake. To test this hypothesis we will use a generalized linear mixed model approach, assuming a binomial distribution and a logit link function. The intervention (peer counseling vs SMS + multimedia website) will be modeled as a fixed effect, and household will be included as a random effect to adjust for within household clustering. As this hypothesis focuses on addressing the best initial intervention, we will include only data collected through the first assessment in this analysis (~ 2 weeks following enrollment). If we find a significant difference (P < 0.05) and the proportion of vaccinated participants is greater in the peer counseling group, then we will conclude that the peer counseling is superior to the SMS + video as an initial vaccination strategy. We will also evaluate whether there is evidence of imbalance between the intervention groups for a variety of covariates including: age, race/ethnicity, sex, zip code, school district, highest education level, vaccine hesitancy, influenza vaccine history, previous COVID-19 illness, household member vaccinated, health insurance type, and perceived COVID-19 risk. If we find some evidence of a difference between the initial intervention groups (P <

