0.10) then those variables will be included in the final multivariable model to estimate the adjusted difference between the interventions. If we find no appreciable difference between the adjusted and unadjusted differences, then we will report the unadjusted difference as our primary result.

Secondary analyses

Our secondary analyses will entail analysis of non-responders as well as subgroup analyses. For those that do not respond to the initial intervention, we hypothesize that switching the intervention will result in the greatest vaccine uptake. We will use the same analytic strategy as in the analysis of the primary outcome, with the exceptions that: (1) we will only analyze participants that did not respond to the initial intervention (i.e., non-responders); and (2) we will test the null hypothesis of no difference in the proportion of participants agreeing to a vaccine between those non-responders that switched (peer \rightarrow SMS + multimedia website, SMS + multimedia website \rightarrow peer) compared to those that did not switch (peer \rightarrow Peer, SMS + multimedia website \rightarrow SMS + multimedia website).

For both the analysis of the initial intervention, and the non-responder analysis we will conduct several subgroup analyses. The subgroup analyses will entail analysis of vaccine uptake stratified by: age (<5, 5-11, 12-17, 18 and older), race (white vs black vs other), school district, health insurance, and gender identity. We will use the same analytical approach as previously discussed for the primary and secondary analyses. Results from these subgroup analyses will enable us to determine whether any of these groups modify the effect of vaccine uptake. Furthermore, estimates from these analyses (in addition to the primary analysis) are critical for understanding the factors that potentially modify vaccine uptake and applying results from our studies to other target populations with similar characteristics^{9,10}.

Sample size estimates

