We powered this study to test the primary hypothesis that an initial intervention of peer counseling will result in greater vaccine uptake compared to the SMS + multimedia website intervention. The sample size needed to test this hypothesis was based on pilot data as well as scientific literature on vaccination uptake. One research study estimated an increase COVID-19 vaccine uptake rate of 3.6% with a text reminder treatment compared to a holdout arm that did not receive a reminder^{11C}. Our listening session data from our community members, felt that receiving vaccination information from a peer would be helpful in becoming vaccinated. Additionally, peer counseling has been noted to increase breastfeeding rates in different race/ethnicity groups of at least 15%. For this reason, we estimate that 15% of participants will agree to a vaccine after having a conversation with a peer. Pilot data available for the study population indicated that the median household size was 1, and for the power analysis we assume 1 person per household but in the main analyses we will include a random effect to account for possible clustering at the household level if there is greater than one person per household. The aforementioned estimates from the literature served as our targets, but due to the inherent uncertainty in the application of results from prior studies to different target populations, we estimated the necessary sample sizes for a range of vaccine uptake-rates (Table 1). Based on these estimates we anticipate that a total drop-out adjusted sample size (peer counseling, SMS + multimedia website) ranging from 285 (increase in vaccine uptake of 12%) to 1113 (increase in vaccine update of 5%) would provide a minimum of 80% power to detect the

effect of interest. These sample sizes are attainable as we already have approximately 1000 unvaccinated individuals that we can contact for enrolment. Additionally, we will be adding more school districts to be eligible for testing. Lastly, we will recruit for enrollment beyond just testing as we utilize our community partners to help us with recruitment.

Increase in % uptake of vaccine	Total sample (unadjusted for drop out)	Total sample size + design effect*	Total sample (adjusted for 20% drop out)			
5%	712	890	1113			
7%	416	520	650			
9%	282	353	442			
12%	182	228	285			

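### The primary estimate is chosen after both the adjusted and unadjusted results are seen, by an undefined criterion that follows a P<0.10 imbalance screen of at least 12 covariates

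*Combined protocol and SAP*

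**What the plan says.** Under E Statistical Plan, Primary analysis, the plan specifies a binomial mixed model with a logit link: "To test this hypothesis we will use a generalized linear mixed model approach". Intervention is the fixed effect, and "household will be included as a random effect to adjust for within household clustering". The decision rule comes next: "If we find a significant difference (P < 0.05) and the proportion of vaccinated participants is greater in the peer counseling group", peer counseling is declared superior.

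Only then do covariates appear: "We will also evaluate whether there is evidence of imbalance between the intervention groups for a variety of covariates". Twelve are named, and the list is introduced as examples, so it is open. For any covariate differing between arms at P<0.10, "those variables will be included in the final multivariable model to estimate the adjusted difference between the interventions". The section ends with the selection rule: "If we find no appreciable difference between the adjusted and unadjusted differences, then we will report the unadjusted difference as our primary result".

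The plan does not say how large an appreciable difference is or on what scale it is judged. That the adjusted estimate is reported otherwise is only implied. Under Secondary analyses, the non-responder comparison inherits the procedure: "We will use the same analytic strategy as in the analysis of the primary outcome", apart from the restriction to non-responders and the switch-versus-stay contrast.

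**The concern.** A primary estimate should be identifiable before the data are seen. Here the two candidates must be compared first, and the criterion is left to judgement at that moment. The scale is open too: the model works in log odds, while the outcome is a percentage and the sample-size Table 1 is in percentage points.

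The trigger is also poorly aimed. Allocation is random, so a significance test of baseline imbalance flags chance differences, and it does so regardless of whether a covariate predicts vaccination. A strongly prognostic covariate that happens to be balanced is left out, although adjusting for it would gain power. Further, the odds ratio is non-collapsible: adding a prognostic covariate to a logit model can move it even when the arms are perfectly balanced. A gap between the two estimates is therefore not clean evidence of confounding.

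At stake are a headline estimate that depends on the data, some forgone precision, and in the smaller scenarios possible instability if a many-level covariate such as zip code or school district is flagged.

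**Working it through.** **1. The plan's sample sizes.** Inputs from Sample size estimates and its Table 1: 80% power, SMS uptake 3.6%, increases of 5 to 12 points. Two-sided alpha of 0.05 and 1:1 allocation are assumed; they reproduce the table.

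Total = 2 × ceil[(1.960 + 0.842)² × (p1q1 + p2q2) / d²]

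- 5 points: 7.849 × (0.0347 + 0.0786) / 0.0025 = 355.7, so 2 × 356 = 712.
- 12 points: 7.849 × (0.0347 + 0.1317) / 0.0144 = 90.7, so 2 × 91 = 182.
- The 7- and 9-point rows give 416 and 282. All four match.
- Design effect 1 + (1.5 − 1) × 0.50 = 1.25 gives 890 and 228; dividing by 0.80 for drop-out gives 1113 and 285.

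This calculation contains no covariates, so it corresponds to the unadjusted model.

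**2. How often the screen flags something.** With 12 independent covariates and correctly sized tests, 1 − 0.9¹² = 71.8%, with 12 × 0.10 = 1.2 flags expected. If the covariates correlate at 0.2 or 0.5 (assumed), the figure is 68% or 53%.

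**3. What the choice does.** Two sets of simulations use 12 independent normal covariates, a P<0.10 screen and plain logistic regression with one person per household, in line with "for the power analysis we assume 1 person per household". The prognostic strengths are assumptions. Set A has one prognostic covariate (odds ratio 1.5, 2.5 or 4.5 per SD; 12,000 trials per setting). Set B gives four covariates a log odds ratio of 0, 0.4 or 0.7 per SD each, so none or four are prognostic (about 2,900–3,000 trials per setting). At 182, some 3–4% of trials were dropped for sparse or failed fits.

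| Share of trials | 712 (3.6% vs 8.6%) | 182 (3.6% vs 15.6%) |
|---|---|---|
| Log odds ratio moves >10%, set A | 5–9% | 15–18% |
| Log odds ratio moves >10%, set B | 3–19% | 13–23% |
| Log odds ratio moves >20%, set B | 1–6% | 4–10% |
| Models disagree on P<0.05, set A | 1.9–3.1% | 3.7–5.5% |
| Models disagree on P<0.05, set B | 1.5–4.4% | 4.2–5.6% |

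The missing threshold matters: in set A at 712, cut-offs of 5%, 10% and 20% are passed in 17–20%, 5–9% and 1–6% of trials. So does the missing scale: at a 10% cut-off, log odds ratio and percentage points give opposite answers in 1–4% of trials. The truly prognostic covariate is flagged in only about 10%, the rate chance alone would give.

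**4. Error rate and power.** Under the null at 712, set A rejects in 4.9–5.1% of trials with the unadjusted model and 5.3–5.5% if whichever model is significant is taken. Set B (8,000 trials, log odds ratio 0.4) goes from 5.0% to 5.4% at 712 and from 3.9% to 4.5% at 182. Shorter null runs (3,000 trials) at 228 and 890 show rises of 0.3 to 0.7 points.

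Power at 712 in set A, for the three prognostic strengths:

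- unadjusted: 79.9%, 80.3%, 80.3%
- the plan's rule with a 10% cut-off: 80.0%, 80.6%, 81.5%
- fixed adjustment for the prognostic covariate: 80.0%, 82.2%, 86.5%

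**5. Sparse categories.** At 228, expected events are 114 × (0.036 + 0.156) = 21.9, about 4 of them in the SMS arm. Study Setting and Populations names seven districts, the timeline adds three to five, and City and County residents may belong to none. For k equal categories (assumed) at a pooled 9.6%, the chance that at least one has no event is 1 − (1 − 0.904^(228/k))^k.

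- k = 7: 21.9/7 = 3.1 events per category, 23%.
- k = 12: 21.9/12 = 1.8 events per category, 85%.

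**The case against.** The strongest reply is that little depends on this rule. The P<0.05 criterion is stated directly after the intervention-plus-household model and before any covariate, so the superiority conclusion need not change with the choice of estimate. The unadjusted estimate is also the default. That stands. A reader might infer that the type I error is seriously inflated, or that analysts may pick the better P value to claim superiority. The documents do not support this: their order points to the unadjusted test, and even taking the better model every time adds only about half a point.

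The figures also need care. They depend on how many covariates are prognostic, which the plan does not give, so the ranges describe the rule and do not predict this trial. Nor is 72% a bound: correlation lowers it, whereas a screen that ignored household clustering would raise it. With an assumed covariate design effect of 1.25–1.5, each flag rate would be 14–18% and the chance of any flag 84–91%. The household random effect was not simulated. Part of the log odds ratio movement is non-collapsibility and should not be read as chance imbalance alone.

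On scale, the percentage outcome and Table 1 lean towards percentage points, but the logit model leaves it open. None of this supplies the missing criterion.

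**Conclusion.** The point holds as a gap in pre-specification. The primary estimate is selected after both candidates are known, with no threshold or scale, and after a screen that does not target prognosis. No other section resolves it. The harm is a data-dependent headline estimate and some forgone precision: against fixed adjustment the rule loses 0 to 5 power points in set A. It is not a material loss of error control, and it does not invalidate the superiority test on its natural reading. The sizes rest on independent participants, independent covariates, none to four of them prognostic, and plain logistic regression. The sparse-category risk concerns the smaller scenarios and depends on how many district categories there are. The change is worth making because it needs only SAP wording.

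**What to change.** Delete the P<0.10 screen and the comparison rule. Name one primary model in advance and apply the P<0.05 rule to it alone. Either choice is acceptable:

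- (a) The intervention-plus-household model already specified. This keeps the Table 1 sample sizes and needs no new item. It gives up up to about 6 power points against fixed adjustment if a covariate is very strongly prognostic (set A), and almost nothing if it is weakly so.
- (b) That model plus a short fixed list of prognostic baseline covariates, for example willingness or hesitancy, and age as a single term. This requires naming the exact item (the Randomization section lists survey topics, not a score), confirming that it is recorded before allocation is known, and a simple rule for missing values. It must stay very small in the smallest scenario: intervention plus two single-term covariates leaves 22/3, about 7 events per coefficient, while age in the four subgroup categories would leave 22/5, about 4.4.

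Report the other model as a sensitivity analysis. State one effect scale. Percentage points would match Table 1, but they do not come directly from a logit mixed model, so specify marginal standardisation and an interval that respects household clustering.

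Apply the same principle to the non-responder analysis, with the switch-versus-stay contrast and the initial arm as a fixed term. Do not enter zip code or district as many-level categories.

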Second, individuals who have not gotten a COVID 19 vaccine will be eligible for the the vaccine trial. This will involve a randomized trial design. More specifically, this study will use a sequential multiple assignment randomized trial (SMART) design.¹² This design will allow participants to be randomized to one of two interventions. If individuals do not seek vaccination after the first intervention, they will again be randomized into the same two interventions. This will allow for testing of both interventions as well as understanding if the use of a more intense intervention (two 'doses') is optimal for vaccine uptake. Figure 1 provides a visual depiction of this study design.

[figure not shown]

Figure 1. SMART design with interventions for vaccine uptake trial

Framework/theory

The interventions for this study have been informed by multiple frameworks. The Michie framework offers the idea that an individual's choice is driven by three components: motivation, opportunity, and capability. The two domains most relevant for this study are opportunity and motivation. All individuals enrolled will be eligible to receive a COVID-19 vaccine. The study will work to ensure the opportunity is available for all individuals to access the vaccine through partnerships with community programs offering COVID-19 vaccination. This study has been designed to understand what dose of an intervention can increase vaccine uptake. We hypothesize that the intervention will increase individual motivation to get a vaccine, which will serve to change participant behavior.

The two interventions have been informed by psychology and health communications. Psychology literature has informed the use of motivational interviewing as a collaborative communication style. Previous literature has shown that motivational interviewing can address concerns and hesitancy in other areas of health behavior. Ultimately, this leads to an increase in desired behavioral outcomes and is a pragmatic, easy to deliver intervention. The other intervention is text message directing the unvaccinated to accessible information. This intervention follows practices that are established by health communications literature, including providing information that is digestible and accessible. The messaging will be based on collaborative communication which was identified by our CAB as the best approach.

Description of milestones and timeline completion

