Once enrolled into the study, each participant will be initially randomized into one of the two intervention groups: (1) SMS + multi-media page, or (2) Phone call with a peer. For household members, randomization will occur at the family unit and all participants will receive the same intervention. All participants will be asked at the start of the study a vaccine-uptake survey regarding the following: their overall willingness to get vaccinated and willingness to vaccinate their children (if applicable); factors that increase and decrease willingness to vaccinate, and their barriers that inhibited their ability to vaccinate.

Within one week of enrollment, the participant/family unit will receive the first intervention. A study team member will follow-up with the participant(s) to determine any changes in vaccination status at the two-weeks receiving their first intervention. If the participant(s) have no changes in their vaccination status, the participant/family unit will undergo a second round of randomization within one week of this follow-up. The same two interventions will be used, so an

individual will receive *either* a second exposure to the same intervention or the intervention that they did not initially receive. After two weeks of the participant's 2nd randomization, a study team member will follow-up a second time to determine vaccination status. During each follow-up session, a study team will provide the same vaccine-uptake survey to the participant and offer to provide vaccine resources on where to obtain a vaccine for the participants. If a participant receives a vaccine an additional phone call will be performed 4 weeks after their first vaccine dose to assess if they completed the primary vaccination series. Compensation of \$100 will be provided for those individuals consenting to this study. This compensation will be provided in allotments of \$50 after completing the consent document and then \$25 after each randomization. If a participant does not need to be randomized a second time, the second \$25 will be provided when learning of the participant receiving their vaccine.

Assessing Vaccine Strategies

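### The SMART is meant to show whether two 'doses' are optimal, but no planned analysis estimates total uptake under any of its four two-step strategies

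*Combined protocol and SAP*

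**What the plan says.** Section C (Study Design) states that "this study will use a sequential multiple assignment randomized trial (SMART) design". It gives the purpose of the second randomisation as testing both interventions and "understanding if the use of a more intense intervention (two 'doses') is optimal for vaccine uptake".

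Section D2 (Randomization) says "each participant will be initially randomized into one of the two intervention groups", SMS with a multimedia page or a peer phone call. If vaccination status has not changed at the two-week follow-up, "the participant/family unit will undergo a second round of randomization within one week of this follow-up", to the same two options. A second follow-up comes two weeks after that.

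Section E (Primary analysis) compares the two initial interventions, and "we will include only data collected through the first assessment in this analysis". Section E (Secondary analyses) opens with "Our secondary analyses will entail analysis of non-responders as well as subgroup analyses". The non-responder analysis leaves out everyone who responded at the first step. It compares those who switched intervention, in either direction, with those who repeated the same one. The subgroup analyses repeat these two contrasts within strata. Section E (Sample size estimates) sizes the trial for the first-step contrast only.

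**The concern.** Two randomisations with two options each embed four strategies: SMS then SMS, SMS then peer, peer then SMS, and peer then peer, with the second step given only to those who have not responded. Whether two 'doses' are optimal is a question about these whole strategies: what share of everyone who starts one is vaccinated by the end of it?

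Neither planned analysis gives that share. The primary analysis stops after the first step. The non-responder analysis starts after it and excludes first-step responders. It also averages escalation (SMS to peer) with de-escalation (peer to SMS), so a large difference between the two interventions at the second step can cancel out. The primary hypothesis is that "the initial strategy of peer counseling will result in the highest vaccine uptake". Without strategy-level results, a two-week first-step difference is the only uptake result available for choosing a complete programme.

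**Working it through.** **Inputs.** From Section E (Sample size estimates and Table 1): SMS uptake 3.6%; increases of 5 to 12 points; 80% power; design effect from an intracluster correlation of 0.50 and cluster size 1.5; 20% drop-out. From Section E (Primary analysis): P < 0.05, taken as two-sided. Assumed, because the documents do not state them: 1:1 allocation at both randomisations, and all second-step uptake rates.

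**The plan's own figure.** Per-arm n = (1.96 + 0.8416)² × [p₁(1 − p₁) + p₂(1 − p₂)] / (p₂ − p₁)².
- 5 points (3.6% vs 8.6%): 7.849 × (0.0347 + 0.0786) / 0.0025 = 355.7, so 356 per arm and 712 in total.
- 12 points (3.6% vs 15.6%): 7.849 × (0.0347 + 0.1317) / 0.0144 = 90.7, so 91 per arm and 182 in total.
- Design effect 1 + (1.5 − 1) × 0.50 = 1.25: 712 becomes 890 and 182 becomes 228. Dividing by 0.80 gives 1113 and 285.

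The 7- and 9-point rows reproduce as well. The stated sizes therefore belong to the first-step contrast alone.

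**Strategy uptake.** With r the first-step uptake and q the second-step uptake in non-responders, total uptake = r + (1 − r)q. Assume first that second-step rates equal first-step rates.

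| Strategy | 12-point row | 5-point row |
|---|---|---|
| SMS then SMS | 0.036 + 0.964 × 0.036 = 7.1% | 7.1% |
| SMS then peer | 0.036 + 0.964 × 0.156 = 18.6% | 0.036 + 0.964 × 0.086 = 11.9% |
| Peer then SMS | 0.156 + 0.844 × 0.036 = 18.6% | 11.9% |
| Peer then peer | 0.156 + 0.844 × 0.156 = 28.8% | 0.086 + 0.914 × 0.086 = 16.5% |

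**What the planned pooled test would see** (12-point row). Non-responders are 0.964 of the SMS arm and 0.844 of the peer arm, 1.808 together.
- Switched: (0.964 × 0.156 + 0.844 × 0.036) / 1.808 = 10.0%.
- Not switched: (0.964 × 0.036 + 0.844 × 0.156) / 1.808 = 9.2%.

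The second-step peer rate is more than four times the SMS rate (15.6 / 3.6 = 4.3), yet the test sees a difference of 0.8 points.

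**Precision of a strategy comparison, without clustering.** With n per first-step arm, variance = [r(1 − r)(1 − q)² + 2(1 − r)q(1 − q)] / n.

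SMS-then-peer vs peer-then-peer, 12-point row, n = 91:
- SMS then peer: (0.0247 + 0.2538) / 91 = 0.00306.
- Peer then peer: (0.0938 + 0.2222) / 91 = 0.00347.
- SE of the difference = √0.00653 = 8.08 points, 95% half-width 15.8. Power for 10.1 points is about Φ(10.1/8.08 − 1.96) = 24%.

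Same contrast, 5-point row, n = 356:
- Variances are (0.0290 + 0.1515) / 356 = 0.000507 and (0.0657 + 0.1437) / 356 = 0.000588.
- SE = 3.31 points, half-width 6.5. Power for 4.6 points is about 28%.

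SMS-then-peer vs peer-then-SMS has a half-width of 13.9 points at 182 and 5.8 at 712.

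**Range over other second-step assumptions**, SMS-then-peer vs peer-then-peer:

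| Second-step rates | 182 analysed | 712 analysed |
|---|---|---|
| Equal to first step | 18.6% vs 28.8%, ±15.8, power 24% | 11.9% vs 16.5%, ±6.5, power 28% |
| Half of first step | 11.1% vs 22.2%, ±13.0, power 38% | 7.7% vs 12.5%, ±5.3, power 43% |
| New intervention at full rate, repeat at half | 18.6% vs 22.2%, ±14.7, power 8% | 11.9% vs 12.5%, ±5.9, power 6% |

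**The case against.** The case against has several parts.

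- **The data are used and could answer the question.** First-step data feed the primary analysis, and second-step data feed the non-responder analysis, which lists all four sequences. A reader might infer that the trial is unable to compare strategies or leaves its second-step data idle. The documents do not support that: only a prespecified way of combining the two steps is missing.
- **The gap is narrower than it looks.** Since total uptake is r + (1 − r)q, reporting non-responder uptake for each of the four sequences beside the primary result would give the point estimates. This stands, but the plan commits only to the pooled contrast, and intervals that respect household clustering would still need a stated method.
- **The hypotheses in Section E each have a matching test**, and the documents never pose the question of starting with SMS and escalating. True. The textual basis for the point is the 'two doses' purpose in Section C, not a general view of what a SMART is for.
- **The tie proves nothing.** A reader might infer that the plan would wrongly favour peer first when SMS-then-peer does equally well. The equality of SMS-then-peer and peer-then-SMS follows by construction from equal rates at both steps and is not a prediction. In that illustration peer-then-peer is the best strategy, and the peer-first strategies average (28.8 + 18.6) / 2 = 23.7% against (7.1 + 18.6) / 2 = 12.9% for SMS-first. The plan's conclusion, limited to the initial strategy, would remain correct.
- **Power is poor.** It is, across the whole range and not just at the small end. That argues for estimation with intervals, not for omission: the planned switch test and subgroup analyses were not part of the sample-size calculation either.

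**Conclusion.** The point holds as a gap in the planned analyses. Section C promises to learn whether two 'doses' are optimal, and Section E estimates uptake over both steps for none of the four strategies. The pooled switch test does not substitute, because under plausible rates it is close to null (10.0% vs 9.2%) while the two interventions differ more than fourfold at the second step.

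The primary test is unaffected and remains valid for its own question. An added strategy comparison would be informative mainly as estimation. For SMS-then-peer vs peer-then-peer, half-widths run from about 5 to 16 points and power from 6% to 43% over the assumptions tried. These figures rest on assumed second-step rates, 1:1 allocation at both randomisations and independent participants. The totals of 182 and 712 are the plan's sizes before its design effect and drop-out allowance, each used with the uptake difference of its own table row.

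**What to change.** Add to Section E (Secondary analyses) a descriptive analysis of uptake by the second follow-up under each of the four strategies, specified before results are seen. It should state:

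1. **Outcome:** vaccinated by the second follow-up, with first-step responders counted as vaccinated.
2. **Weights:** the inverse of the actual randomisation probabilities. If both randomisations are 1:1, first-step responders get weight 1/0.5 = 2 and count in both strategies of their arm; re-randomised non-responders get 1/(0.5 × 0.5) = 4. State both allocation ratios.
3. **Unclear cases:** how participants lost to follow-up and classed as unable to determine enter the weighting, given the planned 20% drop-out. Also state how families in which only some members respond are handled, since re-randomisation is by participant or family unit.
4. **Reporting:** four proportions with household-robust intervals. Name SMS-then-peer vs peer-then-SMS, and SMS-then-peer vs peer-then-peer, as the contrasts of interest. Report them as estimates outside the primary error rate, with no claim of equivalence unless a margin is prespecified.

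The cost is SAP text and analysis work. The rules for missing status and mixed-response families need some thought. No extra participants, visits or data are required. The drawback is low precision at every planned sample size, which the text should acknowledge.
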